5.1.3 Screening Assessments

Inclusion / Exclusion Criteria

Sections 4.1.1 & 4.1.2.

Medical History

Medical History including prior diagnosis, prior oncological disease, prior treatment (including chemotherapy & surgery) and concomitant diseases will be recorded.

Demographics

The date of birth and gender will be recorded.

The WHO performance status (Appendix 1).

Concomitant Medication

These will be recorded in CRFs as per section 9.4.

Physical Examination

An abdominal exam and cardiorespiratory exam will be performed.

Vital Signs

Temperature will be recorded. Resting pulse and blood pressure (BP) measurements will be taken after the participant has been in a sitting position for at least five minutes.

Height & Weight

Body Surface Area (BSA) and Body Mass Index (BMI) will be calculated

Haematology & Biochemistry Tests

- Full Blood Count (FBC); including Haemoglobin (Hb), white blood cells (WBC) with differential count (neutrophils and lymphocytes), and platelets
- Biochemical profile; including sodium, potassium, calcium, phosphate, urea, creatinine
- Liver profile; including total protein, albumin, bilirubin, ALP, AST and/or ALT and LDH
- Group & Save (as standard for surgical candidates, date of valid test to be recorded on CRF, not blood group)
- Clotting Studies; including PT and APPT

Urinary Tests +/- Pregnancy Test

Tests to be performed will be:

- Urinalysis by dipstick.
- In women of childbearing age, a serum or urine Human Chorionic Gonadotropin (HCG) pregnancy test

ECG Test

A 12-lead ECG will be taken for each participant. The eligibility of participants with abnormal AND clinically significant results must be confirmed.

Echocardiogram

An echocardiogram must be performed at baseline to assess LVEF. The test will only be repeated if clinically indicated.

Pre-operative Anaesthetic Assessment (ASA Classification)

A pre-operative assessment will be performed by a suitably trained doctor or nurse, usually in consultant anaesthetist-lead clinic. During this time the previous investigations (as per standard departmental practice) will be reviewed and a decision made if the participant can proceed with a General Anaesthetic. The date and outcome of the assessment (ASA classification) will be recorded.

5.1.3.1 Ultrasound Screening Assessment

A focused diagnostic ultrasound scan will be performed in order to choose suitable tumour area(s), which are easily identified on ultrasound and amenable for biopsy. For participants in both Parts I and II, a single liver tumour amenable to intervention will be targeted. The tumour selected for intervention will be treated with a combination of ThermoDox® and FUS. Refer to section 5.4.3 for more information on the FUS intervention.

As assessed at the Ultrasound session, in order to proceed with the study, the participant must:

1. Have one or more incurable (unresectable, non-ablatable-for cure) liver tumours of size 1cm or greater, which is amenable to ultrasound-guided biopsy
2. Have the total volume to be treated no larger than either removal of 3 hepatic segments or removal of more than 30% of total liver volume (as per maximum surgical limit)
3. Be an appropriate candidate for FUS with consideration given to the following factors:
 - a. Overall health of liver
 - b. Absence of significant cirrhosis
 - c. Absence of significant ascites
 - d. Ultrasound path free of previous radiotherapy or scar tissue
 - e. Ultrasound path free of overlying skin ulceration

In some circumstances, if a participant is found to be ineligible for Part I of the study due to anatomical tumour location, they may still be eligible for Part II. This is because real-time temperature monitoring is not required in Part II and thus the anatomical position of a given tumour area may be more amenable to delivery of the intervention.

5.2 Evaluations during the intervention (d-1 to d2)

Evaluations on day -1 (pre-Intervention day)

- Dose of oral dexamethasone given as pre-medication (section 5.5.2 & 9.3)
- Baseline scans (Usually on d-1 but may be performed from day -7 to day 1 provided before intervention):
 - Liver MRI/MR -Spectroscopy
 - Liver pCT

- Whole body FDG PET-CT

Evaluations on day 1 (intervention day)

- Confirm d-1 pre-medications were given.
- Day 1 pre-medications given
- Confirmatory portable ultrasound to confirm tumour location before patient anaesthetised
- General anaesthetic start and finish time
- Dose of ThermoDox® administered, start and finish time
- Start and finish time of final FUS exposure and FUS parameters
- Thermometry data (Part I only)
- Bloods samples for pharmacokinetics (Pre-Treatment, Unreleased and Released plasma samples)
- Biopsy samples for assay quantification \pm microscopy:
 - Part I: Pre-Treatment, Unreleased, Released
 - Part II: Released
- Adverse event monitoring

Evaluations on day 2 (recovery day)

- Physical exam
- Vital signs: Temperature, resting pulse and blood pressure (BP) after participant has been in a sitting position for at least five minutes
- Full Blood Count (FBC); including Haemoglobin (Hb), white blood cells (WBC) with differential count (neutrophils and lymphocytes), and platelets
- Biochemical profile; including sodium, potassium, calcium, phosphate, urea, creatinine
- Liver profile; including total protein, albumin, bilirubin, ALP, AST and/or ALT and LDH
- Post-treatment Liver MRI/MR-Spectroscopy (within 36 hours, and ideally within 24 hours, of intervention¹⁸)
- Adverse event monitoring

5.3 Follow-up and end of study evaluations (within 60 days)

Follow-up 1: Day 15 (± 3 day tolerance)

Parts I & II:

- Full Blood Count (FBC); including Haemoglobin (Hb), white blood cells (WBC) with differential count (neutrophils and lymphocytes), and platelets
- Biochemical profile; including sodium, potassium, calcium, phosphate, urea, creatinine
- Liver profile; including total protein, albumin, bilirubin, ALP, AST and/or ALT and LDH
- Adverse event monitoring

Follow-up 2: Day 30 (+7 not <30)

Parts I & II:

- Adverse event monitoring
- Concomitant medication recording
- Full Blood Count (FBC); including Haemoglobin (Hb), white blood cells (WBC) with differential count (neutrophils and lymphocytes), and platelets
- Biochemical profile; including sodium, potassium, calcium, phosphate, urea, creatinine
- Liver profile; including total protein, albumin, bilirubin, ALP, AST and/or ALT and LDH

Follow-up Scans: From Day 12 - Day 60 post-intervention as defined in the summary of schedule events (one set of scans at 4 weeks follow-up, the other being flexibly timed in accordance with emerging radiological data from previous study participants)

Parts I & II:

- Maximum of two follow-up Liver MRI/MR-Spectroscopy scans
- Maximum of two follow-up Liver pCT scans
- Maximum of two follow-up whole body FDG PET-CT scans

¹⁸ The time of intervention is defined as the time at which the final FUS exposure is complete

If a participant is withdrawn from the study following the intervention, adverse event recording should continue for 30 days post-intervention. No other follow-up evaluations will be required.

5.4 Trial Procedures

5.4.1 Preparation for Intervention

Part I and Part II

Day -1 (pre-Intervention):

- The participant attends the day before intervention and is given the first dose of oral premedication within 24 hours of the procedure. If required, the patient may be admitted for the pre-medication and stay in hospital until completion of evaluations on Day 2 (see section 5.2 & 5.3 for evaluations).

Day -1 (pre-Intervention) or Day 1 (Intervention):

- The liver tumour identified for intervention in the Ultrasound Session is correlated with both MRI and CT images and may be re-examined by ultrasound in advance of anaesthetising for the intervention.

5.4.2 Intervention

During the intervention the following people are usually present: the Clinical Investigator and/or Co-investigators, anaesthetist, anaesthetic Operating Department Practitioner (ODP), specialist oncology nurse, trained HIFU specialist, Radiologist for biopsy, Radiology nurse and, in Part I, research engineer for real-time data acquisition.

The participant is intubated and anaesthetised. Antibiotic prophylaxis is given on induction. The participant is positioned over the HIFU machine optimally to allow access via the HIFU transducer across the water-bath and access to insert the coaxial needle for taking biopsy or monitoring temperature. At the time of coaxial needle insertion the skin over the puncture area is shaved if necessary, prepared appropriately and a sterile drape is applied.

A detailed Ultrasound Session will have taken place previously (section 5.1.3.1). Further ultrasound planning occurs immediately prior to intervention. This includes three-dimensional tumour evaluation using the diagnostic ultrasound component of the device that will be used to administer FUS exposure. The non-mobile HIFU therapeutic device is located in a purpose-built unit on the Churchill Hospital site and consequently all intervention will take place in this unit.

The HIFU therapeutic device is used to generate hyperthermia in the contoured region of the target tumour using optimised levels of FUS. More information on the FUS procedure can be found in section 5.4.3.

The participants' liver tumours are treated with a combination of FUS and/or ThermoDox® as determined in the Ultrasound Session (section 5.1.3.1). Intervention is performed under General Anaesthetic and the participant is kept in overnight for monitoring following the procedure.

Part I

For each participant in Part I, the optimal FUS exposure parameters to achieve the desired range of mild hyperthermia (and consequent ThermoDox® release) will be determined. The power (watts), duty cycle (or continuous) and duration of exposure will be varied to optimise the temperature response at the tumour site and with a view to achieving targeted doxorubicin delivery.

Day 1 (intervention):

- A co-axial biopsy needle is positioned through the sterile field into the centre of tumour targeted for intervention, under ultrasound guidance.
- A Pre-Treatment Biopsy of the tumour is taken via the co-axial needle, and used as a baseline prior to any intervention, along with the Pre-Treatment blood sample.
- A clinically approved thermometry device is then positioned through the co-axial needle to the target area and is used to obtain real-time thermometry measurements during the FUS exposure.
- The HIFU therapeutic device is aligned to the thermometry device using short test exposures of FUS.

- The tumour area is then exposed to varied and considered FUS parameters (section 5.4.3) until the thermometry confirms that the target range of mild hyperthermia has been achieved within the tumour(*).
- In addition to the FUS exposure parameters (power (watts), duty cycle, duration of treatment) and associated thermometry data, the location of tumour (liver segment) and patient BMI will be recorded for each intervention.
- The thermometry device is then replaced and a cool-down period allows the tumour to return to body temperature.
- Once the tumour has returned to normothermia, the prescribed dose of ThermoDox® is infused over a duration of 30 minutes.
- A second Unreleased Drug Biopsy of the target area is then taken via the coaxial needle (Note: ThermoDox® is circulating at this point, but not yet activated). The corresponding Unreleased Drug blood sample is also taken at this stage for pharmacokinetic analysis within 15 minutes of infusion end.
- The tumour area is then re-exposed to FUS using the exposure parameters identified earlier as being suitable to generate mild hyperthermia within the tumour. During this second FUS exposure, ThermoDox® is circulating between therapeutic and peak levels.
- After completion of the final FUS exposure, a final Released Drug biopsy is taken via the co-axial needle with the corresponding Released Drug blood sample.
- Before removing the coaxial needle, a Gelfoam® (or equivalent) plug embolization of the needle track is applied through the needle to minimise bleeding risk [47].

*Note that with increasing experience, the study team may elect to omit the step of pre-heating the tumour prior to drug delivery (1st FUS exposure) and drug infusion may be commenced shortly after alignment.

The steps of intervention of the liver tumour in Part I are summarised in Figure 4.

The paired Pre-treatment, Unreleased and Released Drug samples (bloods and biopsies) are sent for analysis in an appropriate laboratory. Please refer to section 7 for more information on sample analysis.

[figure not shown]

Figure 4: Timeline for combination exposure of the target liver tumour in Part I (not to scale, total plasma doxorubicin PK curve is for illustrative purposes to demonstrate anticipated PK trend and is not based on actual PK data)

Part II

The optimised FUS acoustic parameters for Part I will be used in Part II. The release of doxorubicin and its therapeutic effect will be investigated. The PI or delegate will have already identified a suitable solitary target liver tumour for intervention at the Ultrasound Session (section 5.1.3.1).

Day 1 (Intervention):

- Preparation as for Part I with the exception that no real-time thermometry data acquisition or pre-intervention biopsies are required in Part II, thus the co-axial needle for biopsy can be inserted after the FUS exposure. Three peripheral blood samples for plasma analysis are taken at the corresponding stages of the intervention (Pre-treatment, Unreleased and Released) as for Part I. The time the blood and biopsy samples are taken must be noted.
- ThermoDox® is infused as per prescribed dose for a duration of 30 minutes.
- After the infusion, the lesion identified for intervention (ThermoDox® release by mild hyperthermia) is exposed to the planned FUS exposure dose, as optimised in Part I, taking into consideration the patient BMI and tumour location (section 5.4.3).
- The non-FUS control tumour, if available, is exposed to ThermoDox® alone without FUS.
- As for Part I, the FUS exposure parameters, location of tumour (liver segment) and patient BMI will be recorded for each evaluation.
- The co-axial needle is inserted and up to two ultrasound-guided Released Drug Biopsies of the tumour receiving intervention are taken, whilst the participant is still under General Anaesthetic. A biopsy is not taken of the control tumour exposed to ThermoDox® only. A corresponding Released Drug blood sample is also taken.
- Before removing the coaxial needle, a Gelfoam® (or equivalent) plug embolization of the needle track is applied through the needle to minimise bleeding risk [47].

The steps of intervention for the liver tumour in Part II are summarised in Figure 5.

[figure not shown]

Figure 5: Timeline for combination exposure of the target liver tumour in Part II (not to scale, total plasma doxorubicin PK curve is for illustrative purposes to demonstrate anticipated PK trend and is not based on actual PK data)

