¹⁰ During the Ultrasound Session feasibility of intervention is confirmed and a target tumour will be selected by ultrasound. Only one screening ultrasound is required.

¹¹ MRI includes the abdomen. Measurements made using the modified RECIST 1.1 criteria.

¹² Liver MRI includes the abdomen. The first Liver MRI/MR Spectroscopy following intervention can alternatively be performed on the same day as intervention, if intervention is in the morning. It should occur within 36 hours of the completion of intervention, and ideally within 24 hours where possible.

¹³ Liver pCT includes the abdomen. Measurements made using CHOI and the modified RECIST 1.1 criteria.

¹⁴ Three blood samples for pharmacokinetics in both Phases I and II (Pre-Treatment, Unreleased drug, Released drug).

¹⁵ Three biopsies in Part I (Pre-Treatment, Unreleased drug, Released drug), two biopsies in Part II (Released drug).

KEY DEFINITIONS

“Intervention” refers to attempted targeted release of ThermoDox® by mild hyperthermia using a focused ultrasound.

The “FUS-targeted tumour” or “target tumour” refers to the liver tumour treated with FUS following ThermoDox® delivery. This is in contrast to the RECIST definition, which defines target tumours as those measurable lesions which are followed through the patient’s treatment course.

A “non-FUS control tumour” refers to a liver tumour receiving ThermoDox® alone which has been selected for radiological follow-up and comparison with the target tumour.

The “desired range of mild hyperthermia” is used in the context of ThermoDox® release in this study and is defined as achieved bulk tissue temperature in the range of 41-47°C

“Optimal FUS exposure parameters” are defined as those combinations of settings on the HIFU device (power, duty cycle and transducer motion plan) which result in an adequate temperature rise to successfully release doxorubicin from the LTSls in the target tumour, without causing direct thermal tissue damage.

An “evaluable participant” is defined as a participant who has received FUS following delivery of ThermoDox® in Part I or II, and for whom it has been possible to evaluate the outcome of the intervention based on biopsy samples, or radiologically.

An “evaluable sample” is defined as a sample for which sufficient material was available for analysis and the analytical technique has provided quantifiable data.

ABBREVIATIONS

AE	Adverse Event
ADL	Activities of Daily Living
ADR	Adverse Drug Reaction

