2 STUDY DESIGN

Phase 1 prospective non-randomised open label single site study to determine whether targeted release of doxorubicin from ThermoDox® ('drug') using mild hyperthermia generated non-invasively by FUS is possible in cancer patients. All participants will receive ThermoDox® and FUS.

The study will run in two parts. Part I will identify optimal FUS exposure parameters for a range of patient BMIs and tumour locations within the liver using real time thermometry data from an implanted thermometry device, such as a thermistor or thermocouple. After at least 5 participants have had the intervention using real-time thermometry, data will be reviewed by the Trial Management Group (TMG) to confirm readiness to proceed without real-time thermometry (Part II). Part II, which does not require implantation of a thermometry device, is designed to reflect how the therapy would be implemented in clinical practice. All evaluable participants from both Part I and Part II will be included in the endpoint analysis.

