3 OBJECTIVES AND ENDPOINTS

The objectives and endpoints for the study are detailed in the following tables. Only evaluable samples will be included in endpoint analysis. All endpoints will be evaluated at the end of Phase II.

The following qualifiers (*, †, ‡ and §) apply to Table 1, Table 2 and Table 3:

* In Part II the Unreleased biopsy is not performed and therefore the average value for all evaluable tumours receiving intervention in Part I is used as a comparison for the two-fold increase from Unreleased to Released biopsy.

† Duration refers to the completion of sample processing but not necessarily the sample analysis. The sample may be stored in a fixed or frozen state and analysed at some time period beyond the specified duration, for example to facilitate batch processing.

‡ Analytical method will only be performed where tissue mass allows. It is expected at most one technique can be performed in addition to the primary endpoint for a given sample. Where biopsy mass falls short, the primary endpoint will be prioritised.

§ Must be shown in at least 50% of evaluable participants.

Primary Objective	Primary Endpoint	How and when data is captured
To determine whether targeted release of doxorubicin from ThermoDox® ('drug') using mild hyperthermia generated non-invasively by focused ultrasound (FUS) is feasible in cancer patients	A demonstrable two-fold increase in*, or value exceeding 10µg/g of, the concentration of intra-tumoural doxorubicin at the treated tumour site following FUS-induced mild hyperthermia § Quantification of intra-tumoural drug release will be achieved by direct analysis of the intra-tumoural biopsy samples using standardised curve(s)	Analytical chemistry performed on a recorded mass of biopsy sample processed within 12 hours of intervention†

Table 1: Primary Objective and Endpoints for the TARDOX Study

Secondary Objectives	Secondary Endpoints	How and when data is captured
Part I only: To determine optimal FUS exposure parameters for a range of participant Body Mass Indices (BMIs) and tumour locations within the liver	Achievement of the desired range of mild hyperthermia in the target tissue as monitored by the implanted thermometry device during FUS exposure	Real-time thermometry monitoring during intervention

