6.1 Patient evaluability and replacement

Patients who are not evaluable for the primary endpoint will be replaced.

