16 STATISTICAL CONSIDERATIONS

16.1 Sample size and power

Evaluable participants will be recruited to either Part I or Part II of the study, up to a maximum of 28 evaluable participants overall. Non-evaluable participants will be replaced (section 6.1).

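### Part I with pre-heating: the protocol does not say what happens if the target temperature is never reached, and an undosed heating failure would be replaced and drop out of the 50% feasibility rate

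*Protocol*

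**What the plan says.** **Order of steps.** In the Part I Day 1 steps of Section 5.4.2, after alignment by short test exposures, FUS settings are varied "until the thermometry confirms that the target range of mild hyperthermia has been achieved within the tumour". A cool-down follows, and then: "Once the tumour has returned to normothermia, the prescribed dose of ThermoDox® is infused over a duration of 30 minutes". A starred note lets the team, as experience grows, leave out the pre-heating and start the infusion soon after alignment. Part II has no thermometry and no pre-heating.

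**Who receives drug.** The synopsis (Study Design) and Sections 2 and 8 state, without exception, that all participants receive ThermoDox.

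**Who counts.** The Key Definitions require an evaluable participant to be "a participant who has received FUS following delivery of ThermoDox® in Part I or II", with an outcome that can be evaluated from biopsy or radiologically. Section 6.1 adds: "Patients who are not evaluable for the primary endpoint will be replaced". Section 16.1 repeats the replacement rule and sets the ceiling: "Evaluable participants will be recruited to either Part I or Part II of the study, up to a maximum of 28 evaluable participants overall". It fixes no split between the Parts.

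**Success rule.** The qualifier on the primary endpoint in Section 3 reads: "Must be shown in at least 50% of evaluable participants". Participants from both Parts are pooled. Section 17.1 has the number of non-evaluable patients recorded, but does not put them into the primary rate.

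**The concern.** The primary objective asks whether release of doxorubicin by FUS-induced mild hyperthermia is feasible in patients. A tumour that cannot be brought into the temperature range is a failure of exactly that. Yet if such a participant stops at the pre-heating step without drug, they cannot have had FUS after ThermoDox. They are therefore non-evaluable, and someone else takes the place.

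The exclusion would also be uneven. In Part II, and in Part I once pre-heating is omitted, a poorly heated participant gets drug and FUS, has a biopsy, and stays in the denominator as a likely failure. The pooled rate would then mix success given that the tumour could be heated with success among all who were treated. Whenever an undosed heating failure occurs, the primary rate moves upwards.

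**Working it through.** **1. Following one participant through the text.** Take a Part I participant with pre-heating whose tumour does not reach the range.

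| Reading | Drug given? | Evaluable? | Effect on primary rate |
|---|---|---|---|
| Step order in 5.4.2 | No route to infusion is written | No (Key Definitions) | Replaced (6.1, 16.1); leaves the denominator |
| Synopsis, Sections 2 and 8 | Yes, all participants | Yes, if the biopsy can be assayed | Stays in, probably as a failure |

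The protocol does not say which row applies. The rest of the check concerns the first row.

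**2. The plan's own figure.** The maximum of 28 cannot be reproduced, because the protocol gives no alpha, power, null rate or expected rate. The rule itself needs at least 0.50 × 28 = 14 successes in 28.

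**3. At the boundary (no assumptions).** With 14 successes in 28 and k replaced heating failures counted back, the rate is 14/(28 + k):
- k = 1: 14/29 = 48.3%
- k = 2: 14/30 = 46.7%
- k = 3: 14/31 = 45.2%

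All three miss 50%. The successes then needed are 15, 15 and 16.

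**4. Chance of meeting the rule (assumptions).** The protocol gives no rates, so assume:
- n₁ of the 28 evaluable participants came through pre-heating. The values 5 and 14 are illustrative; 5 is also the minimum number with thermometry before the Part II review in Section 2.
- A fraction f of pre-heated participants fails to reach the range and is not dosed.
- 60% of all others succeed.

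Formulas:
- Expected removals: n₁ × f/(1 − f)
- Expected rate with removals counted: 28 × 0.60/(28 + removals)
- Chance as the plan counts: P(X ≥ 14), X ~ Bin(28, 0.60) = 0.898
- Chance with removals counted: k is negative binomial (failures before n₁ heated participants), and the rule needs X ≥ (28 + k)/2, rounded up

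| n₁ | f | Expected removals | Rate, counted | Chance, as planned | Chance, counted |
|---|---|---|---|---|---|
| 5 | 10% | 0.56 | 58.8% | 0.898 | 0.860 |
| 5 | 20% | 1.25 | 57.4% | 0.898 | 0.820 |
| 5 | 30% | 2.14 | 55.7% | 0.898 | 0.767 |
| 14 | 10% | 1.56 | 56.8% | 0.898 | 0.803 |
| 14 | 20% | 3.50 | 53.3% | 0.898 | 0.683 |
| 14 | 30% | 6.00 | 49.4% | 0.898 | 0.515 |

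The table recounts one recruited cohort of 28 + k people. If heating failures instead take up places within a total of 28, the pre-heated places succeed with probability 0.60 × (1 − f) and the rest with 0.60. The chance is then P(Bin(n₁, 0.60(1 − f)) + Bin(28 − n₁, 0.60) ≥ 14). This gives 0.875 and 0.850 for n₁ = 5 at f = 10% and 20%, and 0.733 for n₁ = 14 at f = 20%. The direction is the same and the drop is somewhat smaller.

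**The case against.** **No passage says that drug is withheld.** Section 5.4.2 gives a planned order and is silent on failure to heat, while three other places say all participants receive ThermoDox. A reader might infer from the step order that drug is given only after confirmed heating and that unheatable participants get none. The documents do not support that as a rule: the general statements point the other way, and the starred note allows infusion without pre-heating. This stands. The defect is an undefined path plus the consequence that the evaluability rules attach to one of its branches.

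**The exposure is limited.** Part II and Part I without pre-heating are untouched. A failure at the second FUS exposure, after the drug, removes nobody. This also stands, and it bounds the size.

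**Heating failures would be visible.** Reaching the temperature range is a separate Part I secondary endpoint, and Section 17.1 records non-evaluable patients. That is true, but neither returns these cases to the primary rate. The synopsis and Section 2 also describe the endpoint analysis in terms of evaluable participants, so it is not certain that they appear in the secondary endpoint.

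**The primary endpoint is worded as concentration following induced hyperthermia**, so some conditioning on heating may be intended. If so, it is not applied evenly, because participants without pre-heating are not screened in this way.

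**Conclusion.** The concern holds in a limited form. The protocol contains two incompatible accounts of what happens when pre-heating does not reach the range. On one of them, its evaluability and replacement rules take a feasibility failure out of the feasibility rate. Any such case biases the primary rate upwards, but the documents do not show that one will occur.

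The size is unknown. One case matters only at the boundary (50.0% against 48.3%). Under the stated assumptions, with 5 pre-heated participants and 10-20% heating failure, the chance of meeting the rule falls from 0.90 to 0.86-0.82. It falls to 0.68 with 14 pre-heated and 20% failure.

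A reader might go further and treat all 28 as pre-heated. With 10-30% heating failure the underlying success rate would be 54% to 42%, and the chance 0.73 to 0.25. The design does not support that as a likely case, since it foresees opening Part II and allows Part I to drop pre-heating. The analysis plan is not at hand, but evaluability and replacement are fixed in this protocol and steer recruitment, so a later plan could not fully undo them.

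**What to change.** 1. The investigators should reconcile the Part I steps in Section 5.4.2 with the statements in the synopsis and Sections 2 and 8 that all participants receive ThermoDox. No rule on giving or withholding drug is proposed here.
2. In the Key Definitions and Section 6.1, state that a Part I participant who began the pre-heating FUS exposure and was not dosed because the target range was not reached counts as not meeting the primary endpoint and is not replaced. The trigger should be the pre-heating exposure, not the short alignment exposures. Otherwise someone stopped during set-up would be counted.
3. State that participants stopped for unrelated technical or anaesthetic reasons may still be replaced.
4. Report the rate among drug-treated participants as a supportive figure.

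The cost is a few sentences in two places. The primary rate may be slightly less favourable, and a few places are not refilled.
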